14.3.1.2 Unsolicited Adverse Events

Table 94: Number and Percentage of Subjects Experiencing Unsolicited Adverse Events with 95% Confidence Intervals by MedDRA System Organ Class and Preferred Term, and Treatment Arm – Safety Population *

		3.75 A/H + A	oup 1 5 mcg 17N9 AS03 =X)	Group 2 7.5 mcg A/H7N9 + AS03 (N=X)		7.5 mcg A/H7N9 + AS03		Group 3 15 mcg A/H7N9 + AS03 (N=X)		15 mcg A/H7N9 + AS03		Group 4 15 mcg A/H7N9 (N=X)		Group 5 45 mcg A/H7N (N=X)	
MedDRA System Organ Class	MedDRA Preferred Term	n	% (95% CI)	n	% (95% CI)	n	% (95% CI)	n	% (95% CI)	n	% (95% CI)				
Any SOC	Any PT	X	xx (xx-xx)	Х	xx (xx-xx)	х	xx (xx-xx)	х	xx (xx-xx)	х	xx (xx-xx)				
[SOC 1]	Any PT														
	[PT 1]														
	[PT 2]														
[SOC 2]	Any PT														
	[PT 1]														
	[PT 2]			. 1	·	. 1.1	. 1			1: .:	1 . 1				

Note: N = number of subjects in the Safety Analysis Population who received any study vaccination. This table presents number and percentage of subjects. A subject is only counted once per PT.

Table 95: Number and Percentage of Subjects Experiencing Unsolicited Adverse Events with 95% Confidence Intervals by MedDRA System Organ Class and Preferred Term, Treatment Arm and Age Stratum – Safety Population *

MedDRA System Organ Class	MedDRA Preferred Term		Group 1 3.75 mcg A/H7N9 + AS03 (N=X)			Group 2 7.5 mcg A/H7N9 + AS03 (N=X)			Group 3 15 mcg A/H7N9 + AS03 (N=X)			N9		15 mcg	roup 4 g A/H7N9 N=X)			Gro 45 mcg . (N=	A/H7N	N9	
		1	9-64	2	≥ 65	1:	9-64	2	≥ 65	1	9-64	2	≥ 65	1	9-64	2	≥ 65	1	9-64	2	≥ 65
		n	% (95% CI)	n	% (95% CI)	n	% (95% CI)	n	% (95% CI)	n	% (95% CI)	n	% (95% CI)	n	% (95% CI)	n	% (95% CI)	n	% (95% CI)	n	% (95% CI)
Any SOC	Any PT	Х	xx (xx- xx)	Х	xx (xx- xx)	Х	xx (xx- xx)	Х	xx (xx- xx)	X	xx (xx- xx)	Х	xx (xx- xx)	х	xx (xx- xx)	Х	xx (xx- xx)	Х	xx (xx- xx)	Х	xx (xx- xx)
[SOC 1]	Any PT																				
	[PT 1]																				
	[PT 2]																				
[SOC 2]	Any PT																				
	[PT 1]																				
	[PT 2]																				

Note: N = number of subjects in the Safety Analysis Population who received any study vaccination. This table presents number and percentage of subjects. A subject is only counted once per PT.

Table 96: Number and Percentage of Subjects Experiencing Unsolicited Adverse Events by MedDRA System Organ Class and Preferred Term, Maximum Severity, Relationship, Treatment Arm and Age Stratum – Safety Population*

MedDRA System Organ Class	MedDRA Preferred Term	Any In	cidence			Sever	ity [1]			Rela	ationship to	Treatme	nt [2]
					Mild		Moderate		vere	Not Related		Related	
		n	%	n	%	n	%	n	%	n	%	n	%
	Gr	oup 1 3.7	5 mcg A/l	H7N9 +	AS03 ((N = X)							
All Subjects													
Any SOC	Any PT	х	XX	х	XX	х	XX	X	xx	X	xx	х	XX
[SOC 1]	Any PT												
	[PT 1]												
	[PT 2]												
[SOC 2]	Any PT												
	[PT 1]												
	[PT 2]												
[repeat for Ages 19-64 and \geq 65]	•	•					•				•	•	•
		[Repea	t for all t	reatme	nt arms	s]							

^[1] For severity, a subject is counted once per preferred term and is summarized according to their highest severity.

^[2] For relationship, a subject is only counted once per preferred term and is summarized according to their closest relationship.

Table 97: Number and Percentage of Subjects Experiencing Non-Serious Related Unsolicited Adverse Events by MedDRA System Organ Class and Preferred Term, Maximum Severity, Treatment Arm and Age Stratum – Safety Population

MedDRA System Organ Class	MedDRA Preferred Term	Any Ir	ncidence			Sever	ity [1]		
				M	lild	Mod	erate	Sev	vere
		n	%	n	%	n	%	n	%
	Group 1 3.75 mcg A/H	7N9 + AS03 (N=X)	•					
All Subjects									
Any SOC	Any PT	х	xx	X	XX	х	XX	х	XX
[SOC 1]	Any PT	х	xx	X	XX	х	XX	х	XX
	[PT 1]								
	[PT 2]								
[SOC 2]	Any PT								
	[PT 1]								
	[PT 2]								
[Repeat for Ages 19-64 and ≥ 65]		•		•	•	•	•	•	•
	[Repeat for all tre	atment arms							
Note: N = Number of subjects in the Safety A	nalysis Population. This table presents numb	er and percent	age of subject	cts.					

[1] For severity, a subject is counted once per preferred term and is summarized according to their highest severity.

Table 98: Number and Percentage of Subjects Experiencing Unsolicited Adverse Events Within 21 Days Post Study Vaccination by MedDRA System Organ Class and Preferred Term, Day Post Vaccination, Treatment Arm and Age Stratum – Safety Population

		Day 1-8 Post Vac 1		Day 9-22 Post Vac 1		Day 1-22 Post Vac 1		Day 1-8 Post Vac 2		Day 9-22 Post Vac 2		Day 1-22 Post Vac 2		Day 1-22 Post Any Vaccination	
MedDRA System Organ Class	MedDRA Preferred Term	n	%	n	n % n % n % n %		%	n	%						
		Group	p 1 3.75	mcg A/l	H7N9 +	AS03, (N=X)								
All Subjects															
Any SOC	Any PT	X	XX	х	XX	X	XX	x	XX	x	XX	X	XX	х	XX
[SOC 1]	Any PT														
	[PT 1]														
	[PT 2]														
[SOC 2]	Any PT														
	[PT 1]														
	[PT 2]														
[Repeat for Ages 19-64 and \geq 65]	1			•			•	•		•		•		•	
		ı	Repeat	for all t	reatmen	t arms]									

Note: N = Number of subjects in the Safety Analysis Population. This table presents number and percentage of subjects. For each time period, a subject is only counted once per PT.

Table 99: Number and Percentage of Subjects Experiencing Non-Serious, Related Unsolicited Adverse Events Within 21 Days Post Vaccination by MedDRA System Organ Class and Preferred Term, Study Vaccination, Treatment Arm and Age Stratum – Safety Population

			y 1-8 Vac 1	Day Post			Day 1-22 Post Vac 1 Post Vac 2 Post Vac 2		Day 1-22 Post Vac 2		Day 1-22 Post Any Vaccinatio				
MedDRA System Organ Class	MedDRA Preferred Term	n	%	n	%	n	%	n	%	n	%	n	%	n	%
		Group	p 1 3.75	mcg A/l	H7N9 +	AS03 (N=X)								
All Subjects															
Any SOC	Any PT	х	xx	X	XX	X	xx	х	xx	х	xx	х	XX	x	xx
[SOC 1]	Any PT														
	[PT 1]														
	[PT 2]														
[SOC 2]	Any PT														
	[PT 1]														
	[PT 2]														
[Repeat for Ages 19-64 and \geq 65]	•	•	•				•		•				•	•	
		ſ	Repeat	for all ti	eatmen	t arms]									

Table 100: Number of Unsolicited Adverse Events by MedDRA System Organ Class and Preferred Term, Day Post Vaccination, Treatment Arm and Age Stratum – Safety Population

		Day 1-8 Post Vac 1	Day 9-22 Post Vac 1	Day 1-22 Post Vac 1	Day 1-8 Post Vac 2	Day 9-22 Post Vac 2	Day 1-22 Post Vac 2	Day 1-22 Post Any Vaccination
MedDRA System Organ Class	MedDRA Preferred Term	# of Events	# of Events	# of Events	# of Events	# of Events	# of Events	# of Events
	(Group 1 3.75 n	ncg A/H7N9 +	AS03 (N=X)				
All Subjects								
Any SOC	Any PT	x	X	X	X	X	X	X
[SOC 1]	Any PT							
	[PT 1]							
	[PT 2]							
[SOC 2]	Any PT							
	[PT 1]							
	[PT 2]							
[Repeat for Ages 19-64 and \geq 65]								
		[Repeat fo	r all treatmer	nt arms]				
Note: $N = Number of subjects in th$	e Safety Analysis Population. T	his table presen	ts number of e	vents; a subject	may be counted	multiple times.		

14.3.2 Listings of Serious and Significant Adverse Events

Table 101: Listing of Serious Adverse Events – Safety Population *

[Implementation Note: This listing is included in the table shells document, as it is included in the body of the CSR. If the event is ongoing (no stop date), indicate "ongoing" in the "Duration" column. If more than one reason is selected for the reason reported as an SAE, list all reasons in the column, separated by a comma. In the "If Not Related, Alternate Etiology" column, merge the 2 data fields for collecting alternate etiology, separate by a colon. In the CSR, Subject ID should be USUBJID (not PATID) for purposes of de-identification.]

Adverse Event	Associated with Vac #	# of Days Post Associated Dose (Duration)	# of Days Post Vac the Event Became Serious	Reason Reported as an SAE	Severity	Relationship to Study Treatment	In Not Related, Alternative Etiology	Action Taken with Study Treatment	Subject Discontinued Due to AE	Outcome	MedDRA System Organ Class	MedDRA Preferred Term
Subject II): , Treatmo	ent Arm: , A	E Numbe	er:								
Comments	:											
Subject II): , Treatmo	ent Arm: , A	E Numbe	er:								
Comments	:		'					•	1			

Table 102: Listing of Adverse Events of Special Interest – Safety Population *

[Implementation Note: This listing is included in the tables section, as it is included in the body of the CSR. If the event is ongoing (no stop date), indicate "ongoing" in the "Duration" column. In the "If Not Related, Alternate Etiology" column, merge the 2 data fields for collecting alternate etiology, separate by a colon.]

Adverse Event	Associated with Vac #	# of Days Post Associated Vac (Duration)	SAE? Severity	Relationship to Study Treatment	In Not Related, Alternative Etiology	Action Taken with Study Treatment	Subject Discontinued Due to AE	Outcome	MAAE	MedDRA System Organ Class	MedDRA Preferred Term
Subject II	D: , Treatm	ent Arm: ,	AE Number	r :							
			SAE: No Mild								
Comments	s:										
Subject II	D: , Treatm	ent Arm: ,	AE Number	·:							
Comments	s:										

Tables with similar format:

 $Table \ 103: \ Listing \ of \ New \ Onset \ Chronic \ Medical \ Conditions - Safety \ Population \ *$

Table 104: Listing of Non-Serious, Unsolicited, Moderate or Severe Adverse Events - Safety Population *

14.3.3 Narratives of Deaths, Other Serious and Significant Adverse Events

(not included in SAP, but this is a placeholder for the CSR)

14.3.4 Displays of Laboratory Results

Table 105: Laboratory Results by Parameter, Maximum Severity, Study Day, Treatment Group and Age Stratum, All Laboratory Parameters – Safety Population *

Treatment Group	Age Stratum	Study Day	N	N*	N	one		ild/ ide 1		erate/ ide 2		ere/ de 3	Mis	ssing
					n	%	n	%	n	%	n	%	n	%
Group 1 3.75 mcg A/H7N9 + AS03	Ages 19-64	Baseline	х	х	X	xx	х	xx	X	xx	х	xx	х	XX
		Day 8												
		Day 22												
		Day 29												
		Max Severity Post Baseline												
	Ages ≥ 65	Baseline												
		Day 8												
		Day 22												
		Day 29												
		Max Severity Post Baseline												
	All Subjects	Baseline												
		Day 8												
		Day 22												
		Day 29												
		Max Severity Post Baseline												
[Repeat for all Treatment Arms]														

Table 105: Laboratory Results by Parameter, Maximum Severity, Study Day, Treatment Group and Age Stratum, All Laboratory Parameters – Safety Population * (continued)

Treatment Group	Age Stratum	Study Day	N	N*	No	one	Mi Gra	ild/ ide 1	Mode Gra	erate/ de 2	Sev Gra		Mis	sing
					n	%	n	%	n	%	n	%	n	%

Note: The "Max Post Baseline" rows indicate the maximum severity experienced by each subject at any time point post baseline, including unscheduled assessments. N* is the denominator for calculating percentages.

N=Number of subjects in the Safety population; N*=Number of subjects who completed the indicated visit.

Tables with similar format:

- Table 106: Laboratory Results by Parameter, Maximum Severity, Study Day, Treatment Group and Age Stratum, Hemoglobin Safety Population *
- Table 107: Laboratory Results by Parameter, Maximum Severity, Study Day, Treatment Group and Age Stratum, Alanine Safety Population aminotransferase (ALT)*
- Table 108: Laboratory Results by Parameter, Maximum Severity, Study Day, Treatment Group and Age Stratum, Total Bilirubin Safety Population *
- Table 109: Laboratory Results by Parameter, Maximum Severity, Study Day, Treatment Group and Age Stratum, Creatinine Safety Population *

Table 110: Laboratory Results by Parameter, Maximum Severity, Study Day, Treatment Arm and Age Stratum, White Blood Cells – Safety Population *

Treatment Group	Age Stratum	Study Day	N	N*	None		Gra	ild/ ide 1 ow)	Gra	ild/ ide 1 igh)	Gra	erate/ de 2 ow)	Gra	erate/ ide 2 igh)	Gra	rere/ ide 3 ow)	Gra	rere/ ide 3 igh)	Mis	sing
					n	%	n	%	n	%	n	%	n	%	n	%	n	%	n	%
Group 1 3.75 mcg A/H7N9 + AS03	Ages 19- 64	Baseline	Х	Х	х	xx	х	xx	х	xx	х	xx	х	xx	х	xx	х	xx	х	XX
		Day 8																		
		Day 22																		
		Day 29																		
		Max Severity Post Baseline																		
	Ages ≥ 65	Baseline																		
		Day 8																		
		Day 22																		
		Day 29																		
		Max Severity Post Baseline																		
	All Subjects	Baseline																		
		Day 8																		
		Day 22																		
		Day 29																		

Table 110: Laboratory Results by Parameter, Maximum Severity, Study Day, Treatment Arm and Age Stratum – White Blood Cells – Safety Population (continued)

Treatment Group	Age Stratum	Study Day	N	N*	None		Gra	ild/ de 1 ow)	Mi Gra (Hi		Gra	erate/ de 2 ow)	Gra	erate/ de 2 gh)	Sev Gra (Lo		Gra	ere/ de 3 igh)	Mis	sing
					n	%	n	%	n	%	n	%	n	%	n	%	n	%	n	%
		Max Severity Post Baseline																		
[Repeat for all Treatment Arms]																				

Note: The "Max Post Baseline" rows indicate the maximum severity experienced by each subject at any time point post baseline, including unscheduled assessments. N* is the denominator for calculating percentages.

N=Number of subjects in the Safety population; N*=Number of subjects who completed the indicated visit.

Table with similar format:

Table 111: Laboratory Results by Parameter, Maximum Severity, Study Day, Treatment Arm and Age Stratum, Platelets – Safety Population *

Table 112: Laboratory Summary Statistics by Parameter, Study Day, Treatment Arm and Age Stratum, White Blood Cells – Safety Population *

Treatment Group	Age Stratum	Study Day	N	Mean	Standard Deviation	Median	Min, Max
Group 1 3.75 mcg A/H7N9 + AS03	Ages 19-64	Baseline	x	XX.X	xx.x	XX	xx, xx
		Day 8					
		Day 22					
		Day 29					
	Ages ≥ 65	Baseline					
		Day 8					
		Day 22					
		Day 29					
	All Subjects	Baseline					
		Day 8					
		Day 22					
		Day 29					
[Repeat for all Treatment Arms]							

Tables with similar format:

Table 113: Laboratory Summary Statistics by Parameter, Study Day, Treatment Arm and Age Stratum, Hemoglobin – Safety Population *

Table 114: Laboratory Summary Statistics by Parameter, Study Day, Treatment Arm and Age Stratum, Platelets – Safety Population *

Table 115: Laboratory Summary Statistics by Parameter, Study Day, Treatment Arm and Age Stratum, Alanine Aminotransferase – Safety Population * (ALT)

Table 116: Laboratory Summary Statistics by Parameter, Study Day, Treatment Arm and Age Stratum, Total Bilirubin – Safety Population *

- Table 117: Laboratory Summary Statistics by Parameter, Study Day, Treatment Arm and Age Stratum, Creatinine Safety Population *
- Table 118: Laboratory Summary Statistics of Change from Baseline by Parameter, Study Day, Treatment Arm and Age Stratum, White Blood Cells Safety Population *
- Table 119: Laboratory Summary Statistics of Change from Baseline by Parameter, Study Day, Treatment Arm and Age Stratum, Hemoglobin Safety Population *
- Table 120: Laboratory Summary Statistics of Change from Baseline by Parameter, Study Day, Treatment Arm and Age Stratum, Platelets Safety Population *
- Table 121: Laboratory Summary Statistics of Change from Baseline by Parameter, Study Day, Treatment Arm and Age Stratum, Alanine aminotransferase (ALT) Safety Population *
- Table 122: Laboratory Summary Statistics of Change from Baseline by Parameter, Study Day, Treatment Arm and Age Stratum, Total Bilirubin Safety Population *
- Table 123: Laboratory Summary Statistics of Change from Baseline by Parameter, Study Day, Treatment Arm and Age Stratum, Creatinine Safety Population *

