9.2 Methods and Timing for Assessing, Recording, and Analyzing Safety Parameters

9.2.1 Adverse Events

Adverse Event (AE): (ICH) E6 defines an AE as any untoward medical occurrence in a patient or clinical investigation subject administered a pharmaceutical product regardless of its causal relationship to the study treatment. An AE can therefore be any unfavorable and unintended sign (including an abnormal laboratory finding), symptom, or disease temporally associated with the use of a medicinal (investigational) product. The occurrence of an AE may come to the attention of study personnel during study visits and interviews of a study recipient presenting for medical care, or upon review by a study monitor.

AEs, including solicited injection site and systemic (subjective and quantitative) reactions, not meeting the protocol-defined criteria for SAEs will be captured on the appropriate data collection form and eCRF. Information to be collected for unsolicited non-serious AEs includes event description, date of onset, licensed study clinician's assessment of severity and relationship to study product and alternate etiology (if not related to study product) (assessed only by those with the training and authority to make a diagnosis and listed on the Form FDA 1572 as the site principal investigator or sub-investigator), date of resolution of the event, seriousness, and outcome. AEs occurring during the trial collection and reporting period will be documented appropriately regardless of relationship. AEs will be followed through resolution.

Any medical condition that is present at the time that the subject is screened will be considered as baseline and not reported as an AE. However, if the severity of any pre-existing medical condition increases, it will be recorded as an AE.

AEs must be graded for severity and assessed for relationship to study product (see definitions below). AEs characterized as intermittent require documentation of onset and duration of each episode. The start and stop date of each reported AE will be recorded on the appropriate data collection form and eCRF.

FDA defines an AE as any untoward medical occurrence associated with the use of a drug in humans, whether or not considered drug related.

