11.6.2 Safety Data

Summaries and analysis of safety data will be presented for the Safety Analysis Population. All summaries and analyses will be presented for all subjects, and by age stratum.

Solicited AEs will be summarized by severity for each day after each study vaccination (Days 1-7 post each study vaccination) and as the maximum severity over all 8 days. Additionally, solicited AEs will be analyzed by taking the most severe response over the follow-up period, dichotomizing into a binary variable (none versus mild, moderate, or severe) and using standard techniques, such as exact confidence intervals, to summarize the proportion of subjects reporting each symptom, any injection site symptom, and any systemic symptom. Summaries of solicited AEs will be presented separately for each study vaccination as well as overall study vaccinations by treatment arm. The proportion of subjects reporting symptoms may be compared between

treatment arms using Chi-square or Fisher's exact test. The proportion of subjects reporting solicited symptoms between the different study vaccinations (i.e., first and second) will be compared using McNemar's test.

Unsolicited AEs will be coded by Medical Dictionary for Regulatory Activities (MedDRA®) for preferred term and system organ class (SOC). The numbers of SAEs, MAAEs, including NOCMCs, and PIMMCs are likely to be small in this trial and will be reported by detailed listings showing the event description, MedDRA® preferred term and SOC, relevant dates (study vaccinations and AEs), severity, relatedness, and outcome for each event. Non-serious unsolicited AEs will be summarized as number and percentage of subjects reporting at least one event in each MedDRA® preferred term and SOC, cross tabulated by severity and relationship to study product. Additionally, the proportion of subjects and exact 95% confidence intervals of AEs in aggregate and by MedDRA® categories will be computed.

Clinical laboratory data will be summarized by severity for each visit and as the maximum over all post-study vaccination visits. Graphical presentations may include box plots.

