3.2. Endpoints

3.2.1. Primary

Safety:

- Occurrence of study vaccine-related serious adverse events (SAEs) from the time of the first study vaccination through approximately 12 months after the last study vaccination.
- Occurrence of solicited injection site and systemic reactogenicity events from the time of each study vaccination through 7 days after each study vaccination.
- Occurrence of clinical safety laboratory adverse events from the time of each study vaccination through approximately 7 days after each study vaccination.

Immunogenicity:

- For HAI and Neut antibodies, percentage of subjects achieving seroconversion against the influenza 2017 H7N9 study vaccine strain (defined as either a prevaccination titer <1:10 and a post-vaccination titer ≥1:40 or a pre-vaccination titer ≥1:10 and a minimum four-fold rise in post-vaccination titer) at approximately 21 days after the second study vaccination (Study Day 43).
- For HAI and Neut antibodies, percentage of subjects achieving titer ≥1:40 against the influenza 2017 H7N9 study vaccine strain at approximately 21 days after the second study vaccination (Study Day 43).
- Geometric Mean Titers (GMTs) of serum HAI and Neut antibodies against the influenza 2017 H7N9 vaccine strain at approximately 21 days after the second study vaccination (Study Day 43).

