9.6. Clinical Laboratory Evaluations

Clinical safety laboratory parameters (WBC, Hgb, PLT, ALT, T. Bili, Cr) will be collected from each subject prior to each study vaccination and approximately 7 days after each study vaccination. These evaluations will be performed by the central clinical laboratory. The grading scale for clinical laboratory evaluations is presented in Table 13. Clinical laboratory evaluations assessed on Day 1 prior to the first study vaccination will be considered as baseline.

The distribution of laboratory results by severity, study day, treatment arm and age stratum will be presented in Table 105, Table 106, Table 107, Table 108, Table 109, Table 110, and Table 111. Descriptive statistics including mean, standard deviation, median, minimum and maximum values by study day will be summarized for each parameter in Table 112, Table 113, Table 114, Table 115, Table 116, and Table 117, and for the change from baseline for each parameter in Table 118, Table 119, Table 120, Table 121, Table 122, and Table 123. Box plots illustrating the change from baseline for each laboratory parameter will be presented in Figure 25, Figure 26, Figure 27, Figure 28, Figure 29, and Figure 30. Subject

visits with abnormal laboratory results, Grade 1 severity or higher, will be presented in Table 124 and Table 125 for Chemistry and Hematology parameters, respectively.

A complete listing of individual clinical laboratory results will be presented in Listing 12 and Listing 13 for chemistry and hematology, respectively, sorted by subject ID, parameter, and visit number.

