14.3.5 Abnormal Laboratory Value Listings (by Subject)

Table 124: Listing of Abnormal Laboratory Results - Chemistry

Subject ID	Treatment Arm	Age Stratum	Sex	Age (years)	Planned Time Point	Actual Study Day	Laboratory Parameter (Units)	Result (Severity)	Relationship to Treatment	If Not Related, Alternate Etiology	Action Taken with Study Treatment	Subject Discontinued Due to Result?

Subject ID	Treatment Arm	Age Stratum	Sex	Age (years)	Planned Time Point	Actual Study Day	Laboratory Parameter (Units)	Result (Severity)	Relationship to Treatment	If Not Related, Alternate Etiology	Action Taken with Study Treatment	Subject Discontinued Due to Result?

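### The planned laboratory tables show grade by visit and do not determine how many subjects had a new or worse grade within about 7 days after each dose, a primary safety endpoint

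*SAP*

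**What the plan says.** SAP 3.2.1 lists as a primary safety endpoint: "Occurrence of clinical safety laboratory adverse events from the time of each study vaccination through approximately 7 days after each study vaccination". Protocol 3.2.1 has the same endpoint. On the reference point, SAP 9.6 says: "Clinical laboratory evaluations assessed on Day 1 prior to the first study vaccination will be considered as baseline". Protocol 9.2.3 names the same baseline.

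For analysis, protocol 11.6.2 says: "Clinical laboratory data will be summarized by severity for each visit and as the maximum over all post-study vaccination visits". The SAP carries this out in Tables 105-111, which have rows for Baseline, Day 8, Day 22, Day 29 and a post-baseline maximum, by arm and age stratum. The footnote to these tables says that the maximum "rows indicate the maximum severity experienced by each subject at any time point post baseline, including unscheduled assessments".

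The other laboratory outputs are continuous summaries (Tables 112-117), continuous changes from baseline (Tables 118-123, Figures 25-30) and listings. Tables 124 and 125 list subject "visits with abnormal laboratory results, Grade 1 severity or higher".

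Neither document says when a graded laboratory value counts as a laboratory AE. The nearest text is protocol 9.2.1. Its AE definition takes in abnormal laboratory values. It treats a medical condition present at screening as baseline rather than an AE, and adds: "if the severity of any pre-existing medical condition increases, it will be recorded as an AE".

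**The concern.** An endpoint worded as occurrence after each vaccination calls for a count of subjects in whom something happened in that window. A by-visit grade table counts subjects who have a graded value on that day, whether or not they already had it before dosing. Graded Day 1 values can be expected: protocol 7.2.1 says that the Day 1 safety results are not available or reviewed before vaccination, and protocol 5.2.3 gives significant baseline laboratory abnormalities as an example of a reason for withdrawal.

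At stake is the within-arm rate reported for a primary safety endpoint. Without a stated rule, the derivation would be left to the author of the study report, after unblinding. SAP 9.3.2 says outright that Table 99 reports a secondary safety endpoint. No table is tied in this way to the primary laboratory endpoint.

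**Working it through.** **1. Does any planned output give the count?**

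- Tables 105-111: grade distribution at each visit, with no cross-tabulation against the subject's own Day 1 grade. The Day 8 and Day 29 rows do cover the scheduled in-window draws.
- Max row of the same tables: also includes the Day 22 draw, taken before dose 2 and 21-28 days after dose 1 (SAP 4.4.5), and unscheduled draws, for which protocol 8.2.12 sets no time limit.
- Tables 112-123 and Figures 25-30: values and changes in value, not grades.
- Tables 124-125: one line per graded subject visit, with no baseline-grade column in the shell. Listings 12-13 also show individual results. A count could be made by hand from these, but none is planned.
- Table 73: no laboratory row.
- Tables 98-99: unsolicited AEs in Days 1-8 after each dose. These would give a windowed count only if laboratory AEs are entered as unsolicited AEs. Protocol 9.1 and SAP 4.5.1 list the two as separate items, and no text settles the routing.

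**2. Do the Baseline and visit rows together fix the count?**

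Take one parameter, all values Grade 1, none missing. Let N be the number of subjects, b the number graded at Baseline, d the number graded at Day 8 and k the number graded at both. Then

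- new = d − k
- k lies between max(0, b + d − N) and min(b, d)
- so new lies between max(0, d − b) and min(d, N − b).

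N = 160 is the planned size of an adjuvanted arm (SAP Section 5). The values of b and d are assumed, because the documents give no Day 1 prevalence.

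| b | d | new, lower | new, upper | as % of 160 |
|---|---|---|---|---|
| 3 | 8 | 8 − 3 = 5 | min(8, 157) = 8 | 3.1 to 5.0 |
| 16 | 16 | 16 − 16 = 0 | min(16, 144) = 16 | 0 to 10.0 |
| 16 | 20 | 20 − 16 = 4 | min(20, 144) = 20 | 2.5 to 12.5 |
| 32 | 38 | 38 − 32 = 6 | min(38, 128) = 38 | 3.8 to 23.8 |

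Identical Baseline and Day 8 rows are thus compatible with no new grades, or with every Day 8 grade being new.

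**3. How large can the overstatement be?**

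The excess of a visit row over the new-or-worsened count consists of subjects whose grade at that visit is no higher than their own Day 1 grade. Each of them was graded on Day 1, so 0 ≤ excess ≤ b. Each 1% of subjects carried in unchanged adds 0.01 × 160 = 1.6 subjects in an adjuvanted arm and 0.01 × 80 = 0.8 in an unadjuvanted arm. The bound applies to visit rows. The Max row can exceed an in-window count by more, because it also admits out-of-window values.

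**4. Does Day 1 alone suffice as the reference for dose 2?**

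No. A subject with grade 0 on Day 1 and Grade 1 at Day 8, Day 22 and Day 29 would be new after dose 1, and would count as new again after dose 2 if Day 29 were compared with Day 1 only. Showing the Day 22 pre-dose grade prevents this.

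**The case against.** The strongest reply is that the new-or-worsened rule is brought in from outside the endpoint. The laboratory grading scales (protocol 9.2.3, SAP Table 13) are fixed thresholds with no reference to baseline, and the sentence in protocol 9.2.1 concerns a medical condition present at screening. That stands: extending it to laboratory grades is reasonable but is an inference, and the word overstate depends on it. A reader might infer that the documents define a laboratory AE as a change from Day 1 and that Tables 105-111 contradict that definition. The documents do not support this, because neither contains such a definition.

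The SAP also does what protocol 11.6.2 prescribes, so there is no departure from the protocol. Day 22 has its own row, so its place in the maximum is visible. The Baseline row sits beside the visit rows, and a graded Day 1 result would appear as its own line in Tables 124-125. The information is therefore collected and recoverable. What is missing is a planned count and a rule for making it.

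The upper limits in the illustration arise only when no Day 1 abnormality persists. In that case the visit row is exactly right and nothing is overstated.

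**Conclusion.** The point holds as a cheap improvement. The planned categorical tables report grade prevalence by visit and a maximum that is not limited to the endpoint window. They do not determine how many subjects had a new or worse grade within about 7 days after each dose. Read as the endpoint result, a visit row can exceed the new-or-worsened count by 0 up to the number graded at baseline. The actual amount cannot be estimated, because the documents give neither Day 1 prevalence nor persistence.

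This rests on two assumptions: that a laboratory AE is read in line with protocol 9.2.1, and that laboratory AEs are not entered as unsolicited AEs. If they are so entered, Tables 98-99 would supply a windowed count.

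A reader might also infer that comparisons between arms are biased or that safety stopping is affected. Neither follows. Randomization balances carried-in grades on average, SAP 9.6 plans no laboratory test between arms, and the halting rule in protocol 9.5 concerns Grade 3 vaccine-related laboratory AEs and does not use these tables. The consequence is descriptive, though it concerns a primary safety endpoint.

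**What to change.** In SAP 9.6, add a shift display by arm and age stratum, per parameter, and per direction for WBC and platelets, separately for each dose:

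- Dose 1: Day 1 grade by worst grade within about 7 days after dose 1, using the Day 8 draw and any in-window unscheduled or early-termination draw.
- Dose 2: the same for the window after dose 2 (Day 29 and any other in-window draw), with Day 1 as the named baseline and the Day 22 pre-dose grade shown, so that a grade already present before dose 2 is not counted as new after it.

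Give the number and percentage of subjects with a new or worsened grade after each dose, per parameter and for any parameter. Build the any-parameter count from the per-parameter results, because a grade pooled over parameters, as in Table 105, can hide a new grade in a second parameter. State that this display reports the primary laboratory AE endpoint. Keep Tables 105-111 unchanged as the summary that protocol 11.6.2 specifies, and record the addition in SAP Section 12, which now says that there are no changes from the protocol analyses.

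The cost is a modest set of extra table pages from data already collected. No visit, sample or clinical rule changes.
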